## EMPIRICAL SPECIFICATION

The main analysis of the primary and secondary outcomes described above will be based on the “intent to treat” impact of the different MomConnect messaging arms. Because of stratified randomized assignment, we expect the only systematic difference between mothers in different study arms to be the type of messaging they receive. The “intent to treat” effect refers to the impact of signing up for MomConnect and being assigned to one of the treatment messaging arms on primary and secondary outcomes, relative to the status-quo arm. Each arm involves a different method of engaging with content about healthy pregnancies. Given the arbitrary nature of defining “treatment compliance” in this context (i.e. mode of engagement varies message to message) - our analysis will focus on estimating average treatment impact among those who signed up for and *were sent* the messages. The ITT estimate is the decision-relevant estimator as this provides a picture of the impact of introducing the program at scale. The analysis of primary and secondary outcomes will follow from the model specified below.

### Primary Specification

For our primary research question, we will estimate the following regression specification in order to understand the impact of each treatment arm on the four primary outcomes (immunizations, ANC visits, knowledge/attitudes index, behavior index):

$$Y_{is} = \alpha + \sum_j \beta_j T_{jis} + \delta_s + \epsilon_{is}$$

- $Y_{is}$  is the midline or endline primary outcome of mother  $i$  in stratum  $s$
- $T_{jis}$  is the treatment indicator for mom  $i$  and treatment arm  $j$  in stratum  $s$ .  $\beta_j$  is the impact of treatment arm  $j$  relative to the status quo model (control).
- $\delta_s$  is a vector of dummies corresponding with each stratum (province by age-range category by weeks pregnant category at time of recruitment)
- $\epsilon_{is}$  is the individual level error term. We will estimate heteroskedasticity-robust standard errors using the Huber-White sandwich estimator.

In primary analysis, we will use the separate specification to test the differences in outcomes between the WhatsApp ARM control arm and each of the two other WhatsApp treatment arms (RCM, and RCM + BCM) as well as the difference between RCM and RCM+BCM and the difference between RCM and RCM-SMS.

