## SAMPLE SIZE

Since we are comparing different versions of MomConnect, it is important that the experiment is well-powered with sufficient sample size to detect reasonably small differences between treatment arms. A sample size of 5,200 completed endline interviews enables the experiment to have 80% power to detect a reasonably small effect size of a 5 percentage point difference in binary outcomes between individual treatment arms.

The table below outlines a summary of the power calculations and the sample sizes for the study:

*Table 4: Sample Sizes*

Sample Sizes	
Per control arm (1 arm) at Endline	1300
Per treatment arm (3 arms) at Endline	1300
Total Sample Size Overall (expected at endline)	5200
Number of MomConnect users to enroll in the study	8667
Minimum detectable effect size between different treatment arms	5 percentage points
Assumptions	
There are around 8,667 women who will register for MomConnect while 16-30 weeks pregnant and consent to the study during the study period. This is based off of MomConnect data from 2022.	
Based on previous surveys with MomConnect users, we expect an endline completion rate of around 60%. Thus, with 8,667 enrolled participants, we should reach the desired sample size of 5,200.	
Based on previous data on the share of babies of mothers enrolled on MomConnect, we are assuming a control group estimate of 68% for full infant vaccination 7 weeks after birth.	
Parameters	
Alpha: the level of statistical significance	0.05 This is the research standard

Power: the probability of avoiding a Type II error ("false negative")	0.80 This is the research standard
Unit of Treatment Assignment	Individual
Predicted Mean of Outcome Variables: the estimated indicator value	0.68 We assume that 68% of the control group will have their children fully immunized with the NDOH-recommended vaccinations from birth to 6 weeks post-birth, measured during an endline interview around 7-10 weeks after birth.

We will have the same power for detecting a 5 pp. increase for our other primary outcome variable, a binary indicator taking on value 1 if a mother completed at least 8 ANC visits as recommended by the WHO and 0 otherwise. Our two secondary outcomes, the knowledge index and the behavior index, we will only measure for 2,200 endline respondents instead of the full sample of 5,200 respondents. With an alpha of 0.05 and power of 0.8, we will be powered to detect a MDES of 0.17 standard deviations for both indices.

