#### Secondary Outcomes

Our secondary outcomes include indices based on a number of questions related to both knowledge of healthy behaviors as well as actual adoption of healthy behaviors. We calculate these two indices using primary data from our endline survey. Other secondary outcomes relate to the user experience of the MomConnect platform, based on both backend data and some survey questions.

The knowledge and behavior outcomes will be coded as two summative indices with equal weights given to the different topic areas of interest. The topic areas and questions within topic areas were determined together with Reach based on the content of MomConnect. This is done for two reasons: first, MomConnect content covers a variety of topic areas, and other than immunizations and ANC visits, no single topic was identified as more important or decision-relevant than others; second, compared to the alternative of analyzing each topic area separately, collapsing discrete topic areas into two indices reduces the risk of false positive results from testing a large number of hypotheses. The success of each treatment arm relative to control will therefore be based on demonstrating impact on administered child immunizations six weeks after birth, the number of ANC visits pregnant women went to during their pregnancy, mothers' knowledge/attitudes, and mothers' behavior.

In the two summative indices, each topic area is given an equal weight in the overall index, regardless of how many questions are included in each topic area. A score multiplier will ensure that each topic area is equally weighted. We

chose to equally weigh each topic because all content areas are an equally important contributor to overall health. To ensure that each topic area has an equal weight, we do the following *for each outcome*:

- Count the number of topic areas (N)
- Count the total number of points that mothers could earn *within* each topic area (S)
- Sum the total number of points *across* all topic areas (T)
- Calculate the overall score per topic area, which is the sum of all points a mom received from survey response (A)

Each topic area score (A) will be multiplied by a multiplier:

$$A * \frac{T}{NS}$$

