To calculate the overall score for the outcome, the above formula will apply to each topic area, and then scores will be summed across all topic areas. Therefore, the overall score for each outcome will be at maximum  $T$  and regardless of how many questions are asked within each topic area, each topic will be given at maximum  $\frac{T}{N}$  points. The overall score will represent knowledge/attitudes or behaviors of healthy behaviors overall (across all topics).

The table below summarizes the primary outcomes across midline and endline:

Table 5: Knowledge and Behavior Indices

Outcome	Definition
Endline Outcomes	
Immunisations	Number of immunisations baby received at birth and 6 weeks after birth (continuous variable with range 0-6)
ANC Visits	Number of ANC visits mother attended at clinic during her pregnancy (continuous variable)
Knowledge of/ Attitudes toward Healthy Behaviors  (Max score = 12)	$((Baby\ danger\ signs\ score\ * \frac{4}{7}) + (Breastfeeding\ score\ * \frac{4}{3}) + (Anemia\ score\ * \frac{4}{5})$ 
where:
 
Baby danger signs score (0-7) = the sum of the following points:
 
 
• 1 point if mothers know that it is dangerous for babies to sleep on their tummies and with a blanket
 
• 1 point if mothers identify that her baby having difficulty eating is a danger sign
 
• 1 point if mothers identify that her baby having difficulty breathing is a danger sign
 
• 1 point if mothers identify that her baby having a high fever is a danger sign
 
• 1 point if mothers recognize that her baby not moving is a danger sign
 
• 1 point if mothers recognize that her baby having a seizure is a danger sign
 
• 1 point if mothers recognize that her baby having jaundice is a danger sign
 
 
Breastfeeding score (0-3) = the sum of the following points:

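### The plan does not settle which outcomes, or how many of them, make an arm successful: four are called primary in some places and two in others, and the FDR family covers only the two

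*Combined protocol and SAP*

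**What the plan says.** **Four outcomes.** Primary Specification sets out to estimate "the impact of each treatment arm on the four primary outcomes (immunizations, ANC visits, knowledge/attitudes index, behavior index". The lead-in to Table 5 reads "The table below summarizes the primary outcomes across midline and endline", and the table then lists immunisations, ANC visits and both indices. The only sentence that defines success is in Secondary Outcomes: "The success of each treatment arm relative to control will therefore be based on demonstrating impact on administered child immunizations six weeks after birth". It goes on to add ANC visits, knowledge/attitudes and behaviour. It does not say whether one, some or all of the four must show an effect.

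**Two outcomes.** Primary Outcomes names immunizations and ANC visits only. Sample Size has "Our two secondary outcomes, the knowledge index and the behavior index", and Secondary Outcomes itself opens with "Our secondary outcomes include indices based on a number of questions". Multiple Hypotheses Adjustments crosses four contrasts with two outcomes to get 8 hypotheses, applies sharpened FDR q-values to them, and calls secondary outcomes exploratory. It promises both corrected and uncorrected p-values but gives no q-value cut-off.

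**Form of the two primaries.** Sample Size powers the trial on full immunization as a yes/no outcome (68% in control) and on "a binary indicator taking on value 1 if a mother completed at least 8 ANC visits". Table 5 instead has "Number of immunisations baby received at birth and 6 weeks after birth (continuous variable with range 0-6" and "Number of ANC visits mother attended at clinic during her pregnancy (continuous variable".

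**The concern.** The labels would matter little if nothing depended on them, but the success sentence includes two indices that the multiplicity section treats as exploratory and leaves uncorrected. Three readings are open: any one of the four outcomes suffices, all four are needed, or only the two FDR-adjusted primaries count. The same data can make an arm a success under one reading and a failure under another. Because no rule is written down, it could be chosen after the results are known. The Research Questions table ties the primary question to national expansion of the most effective version, so the verdict has consequences.

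**Working it through.** **1. The plan's own figures reproduce.**
- Multiplicity: 1 − 0.95^8 = 0.337, stated as about 34%.
- Sample size: 0.68 vs 0.73, two-sided 0.05, 80% power needs 1,305 per arm; 1,300 are planned, giving power 0.799. Enrolment: 5,200/0.60 = 8,667.
- Indices: 2,200/4 = 550 per arm. The minimum detectable effect is (1.960 + 0.842) × √(2/550) = 0.169 SD, stated as 0.17.

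**2. Counting the tests.** The success sentence covers every treatment arm against control on four outcomes: 3 × 4 = 12 tests. The 8-test family contains ARM vs RCM and ARM vs RCM+BCM on two outcomes: 2 × 2 = 4. Outside it are 3 × 2 = 6 index tests and 2 tests of RCM-SMS vs ARM, 8 in all. The family's other four tests compare active arms with each other. If only the contrasts listed at the end of Primary Specification are counted, RCM-SMS vs ARM drops out and the ratio is 4 of 8.

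**3. Simple bounds for one arm** (independent outcomes, every test unadjusted at two-sided 0.05, 80% power each).
- Any of four: false positive 1 − 0.95^4 = 18.5%; power 1 − 0.2^4 = 99.8%.
- All four: false positive 0.05^4 = 0.0006%; power 0.8^4 = 41.0%.

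**4. Simulation closer to the plan.** Four equal arms with shared-arm contrasts; the 8 primary tests adjusted by the two-stage Benjamini-Krieger-Yekutieli procedure; indices tested unadjusted at two-sided 0.05; success counted only for effects favourable relative to ARM; 200,000 runs per setting. Effects are those used for power: 0.05/√((0.68×0.32 + 0.73×0.27)/1300) = 2.80 standard errors for a primary and 0.17/√(2/550) = 2.82 for an index; 2.80 was used throughout. The ANC outcome is given the same power because Sample Size says so. Assumed, because the plan is silent: common outcome correlation 0 to 0.8 and q-value cut-off 0.05.

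| Rule | Correlation 0 | 0.3 | 0.6 | 0.8 |
|---|---|---|---|---|
| *No arm works: either WhatsApp arm called successful* | | | | |
| Any of four | 10.2% | 9.5% | 8.3% | 7.2% |
| Either FDR-adjusted primary | 1.35% | 1.38% | 1.38% | 1.31% |
| All four | 0.00% | 0.01% | 0.13% | 0.46% |
| *Only RCM+BCM works: RCM+BCM called successful* | | | | |
| Any of four | 99.5% | 97.0% | 92.8% | 88.6% |
| Either primary | 86.2% | 81.9% | 76.8% | 73.2% |
| Both primaries | 53.7% | 56.9% | 60.4% | 63.5% |
| All four | 34.4% | 43.7% | 52.5% | 59.4% |

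For a single arm, any-of-four gives 5.7% down to 4.1% when nothing works. At correlation 0 the two uncorrected indices alone give 1 − 0.975² = 4.9%, so they account for most of it. These figures are below the 18.5% in step 3 because the primaries are now adjusted and only favourable results count. If both primaries are required, false success for RCM+BCM is about 0.01–0.4%.

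**5. Sensitivity.** With a cut-off of 0.10, the no-effect figures become 8–12% (any of four), 2.7–2.9% (either primary) and at most 0.8% (all four). If the 2,200 index respondents are a subset of the 5,200, primary-index test correlations shrink by √(2200/5200) = 0.65. At outcome correlation 0.8, any-of-four then gives 7.8% false success and 91.9% power, and all-four 0.15% and 53.8%. All of these lie within the ranges above.

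**The case against.** Multiple Hypotheses Adjustments is the section that deals with inference and scale-up. It fixes the family, the contrasts and the method, and says secondary outcomes are exploratory. Three sections agree on two primaries, and the success sentence stands under a heading that calls the indices secondary. That sentence joins its four outcomes with a conjunction, so a joint reading is the more natural one, and under it false success is negligible. The multiplicity section does not speak of success at all, so the two passages might coexist as broad evidence on four outcomes and formal correction on two. RCM-SMS vs ARM is never listed as a contrast, and alpha of 0.05 is an obvious default for the cut-off.

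Much of this stands. Two primaries are probably what was meant, no passage states the any-of-four rule, and 12 is not the only defensible count. But the multiplicity section neither amends nor mentions the success sentence, which applies to every arm and gives no count. The joint reading is costly too: under it a truly effective arm is called successful in only 34–59% of trials. An alpha for single tests is also not a stated q-value threshold.

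**Conclusion.** The concern holds. The operative text contradicts itself on whether there are two or four primary outcomes and on whether the primaries are binary or counts. It states no rule for success, and 4 of the 12 implied arm-versus-control tests are corrected (4 of 8 on the narrower count). Across the readings, false success for a WhatsApp arm runs from at most 0.5% to 7–10%, and the chance of recognising an effective RCM+BCM arm from 34–59% to 89–99%. These figures rest on the assumed correlations, the 0.05 cut-off and the effects used for power. The size of the gap changes with them, but a gap remains at every setting tried. The arm estimates themselves are unaffected. This should be fixed before the outcome data are seen.

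**What to change.** - In the Table 5 lead-in and Primary Specification, name immunizations and ANC visits as the only primary outcomes, in the binary form that Sample Size is powered on. Counts can be kept as supporting analyses.
- Rewrite the success sentence in Secondary Outcomes so that success against control is judged on the FDR-adjusted results for those two outcomes. State the q-value cut-off (for example 0.05) and whether one or both outcomes are required.
- Report the two indices as secondary and exploratory, outside the success rule.
- Either limit the success sentence to the two WhatsApp arms, which matches the scale-up decision and the 8-test family, or add ARM vs RCM-SMS on both primaries for a 10-test family. The second option fits better with the Research Questions table, which asks about every version.

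**Cost.** Wording only, no new data. A favourable index result could no longer support a success claim by itself, and under the WhatsApp-only option SMS vs ARM is a reported estimate without a success verdict. The 10-test option changes power per RCM+BCM primary test (correlation 0, cut-off 0.05) from 70% to 66% if only RCM+BCM works, from 79% to 74% if both WhatsApp arms work, and from 70% to 73% if all three work. A stated hierarchy that keeps the indices in the success rule would also resolve the conflict, but the FDR family and the statement that secondary outcomes are exploratory would then have to change.

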## RECRUITMENT & RANDOMIZATION PROCEDURE

Pregnant women presenting at public health facilities across South Africa are asked by nurses, in accordance with national health guidelines, if they would like to join the MomConnect platform. This process has successfully registered 60% of pregnant women across the country (Benjamin et al. 2018). The recruitment process for this study will follow the same procedure and is unchanged by the study.

Women will register for MomConnect at a health facility by filling out a USSD recruitment survey. The survey asks specific questions about each pregnant woman. From the recruitment survey, we will learn the gestational age of pregnant women, how old they are, and which province they are from. Mothers will then be asked if they would like to take part in a research study to improve the MomConnect service and will be sent a consent message via WhatsApp. Consenting participants will then be assigned to different strata (one of three categories for gestational age: 16-20 weeks, 21-25 weeks, 26-30 weeks; one of two categories for age: 30 and under, over 31; and one of nine categories for province). Next, they will be sorted into one of 54 strata according to their unique combination of weeks pregnant, age, and province. Because recruitment is occurring on a rolling basis, we use sequential randomization within strata to improve balance within strata, across study arms. Participants will then be assigned one of the four messaging arms according to an ex-ante random schedule within each stratum. In this way, there will be a similar way of women assigned to each of the four arms within each stratum.

After consent and randomization participants will be invited to a (non-mandatory) baseline survey via WhatsApp (or USSD for the RCM-SMS arm) and will start to receive content based on which of the four study arm message models they were randomly assigned to. Women who do not give consent to be part of the study will receive the status-quo WhatsApp MomConnect service (equivalent to the Control arm) and be excluded from the study.

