## Subgroup analysis

We will also do some exploratory subgroup analysis based on the following characteristics:

1. **Age:** We might expect mothers who are above 35 (advanced maternal pregnancy) to act differently than mothers who are below 35 given the higher risks associated with pregnancies for mothers above 35.
2. **The number of children the mom has:** We might expect first-time mothers to rely more on MomConnect than incumbent mothers who could pull from previous experience.
3. **Education level:** Since education levels are associated with socioeconomic status, we might expect mothers with less formal education to have less access to knowledge and resources on how to adopt healthy behaviors
4. **Income quartile:** We might expect mothers from poorer households to have less access to knowledge and resources on how to adopt healthy behaviors.
5. **Province:** The health service infrastructure differs strongly across South African provinces. We will explore in which provinces MomConnect is particularly effective.
6. **Weeks pregnant at sign-up:** The earlier in their pregnancy mothers sign-up with MomConnect, the longer they are exposed to messaging. We would therefore expect mothers signing up earlier to see larger benefits. We will use the stratification bins for weeks pregnant for this analysis.

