### Multiple Hypotheses Adjustments

The most relevant decision from this study to inform scale-up of the program will be informed by which WhatsApp treatment arm is best for key primary health outcomes. We will test the following 8 null hypotheses:

- The difference in  $outcome_i$  between ARM and RCM is zero
- The difference in  $outcome_i$  between ARM and RCM + BCM is zero
- The difference in  $outcome_i$  between RCM and RCM + BCM is zero
- The difference in  $outcome_i$  between RCM and RCM + SMS is zero

where the subscript  $i$  captures the two main outcomes, immunizations and ANC visits.

Given that there are multiple hypotheses to test, standard statistical significance levels ( $\alpha = 0.05$ ) would likely result in finding significant outcomes by chance alone. Indeed, the probability of finding at least one false significant result (rejecting the null when it is true), would be  $1 - (1 - 0.05)^8 = \sim 34\%$ .

[figure not shown]
To correct for this, we will adjust for multiple hypotheses by applying a false discovery rate adjustment (FDR) following Benjamini et al. (2006). In particular, we will use the sharpened q-values discussed in Anderson (2008). This correction will control for the expected proportion of Type 1 errors. In our analysis, we report both corrected and uncorrected p-values.

These multiple hypothesis adjustments will focus on analysis of the four treatment arms and two primary outcomes specified given that these hypotheses affect potential scale-up decisions. Secondary outcomes will be exploratory.

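### The primary regression adjusts only for banded gestational age and age, although both are recorded for every woman before randomisation; adding the finer values is a free but modest gain in precision

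*Combined protocol and SAP*

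**What the plan says.** The Primary Specification regresses each outcome on arm indicators and a stratum term that "is a vector of dummies corresponding with each stratum (province by age-range category by weeks pregnant category at time of recruitment". No other covariate appears. The attrition check reuses these controls, and no other adjusted model is specified.

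Under Recruitment & Randomization Procedure, the strata are three gestational bands (16–20, 21–25 and 26–30 weeks), two age bands split at about 30, and nine provinces, which makes 54 cells. The same section says that from the registration survey "we will learn the gestational age of pregnant women, how old they are, and which province they are from". That survey comes before consent, stratification and allocation.

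Two other sections suggest that the values are held more finely than the bands. The post-stratification weights under External Validity and Gestational Age are built from gestational age. The Subgroup analysis section cuts age at 35, which the stratum boundary cannot supply. That section also lists "The number of children the mom has" and education level as exploratory subgroup variables, without saying which survey collects them.

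**The concern.** Variation in gestational week and age within a band stays in the error term, even where it predicts the outcome. Adjusting for prognostic values fixed before randomisation brings negligible bias at this sample size and can narrow the intervals.

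The design has no planned reserve. It claims "80% power to detect a reasonably small effect size of a 5 percentage point difference in binary outcomes between individual treatment arms", and the calculation below gives almost exactly that. A small gain in precision that needs no data collection is therefore worth taking. It also has to be written down in advance, because covariates added after the results are known invite suspicion of a search for a favourable model.

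**Working it through.** **Inputs from the plan (Sample Size, including Table 4)**
- Control proportion 0.68: "we are assuming a control group estimate of 68% for full infant vaccination 7 weeks after birth".
- Difference of 5 points, so 0.68 against 0.73.
- Alpha 0.05 and power 0.80. Sidedness is not stated. I take two-sided, because the nulls are of the form that a difference "between ARM and RCM is zero".
- "A sample size of 5,200 completed endline interviews" over four equal arms, so 1,300 per arm.

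**Reproducing the plan's figure**
- Mean proportion = (0.68 + 0.73)/2 = 0.705.
- Null term: 1.960 × √(2 × 0.705 × 0.295) = 1.960 × 0.6449 = 1.264.
- Alternative term: 0.842 × √(0.68 × 0.32 + 0.73 × 0.27) = 0.842 × 0.6440 = 0.542.
- n per arm = (1.264 + 0.542)² / 0.05², which gives 1,305 before rounding of the terms. The plan has 1,300.
- Power at 1,300: z = (0.05 × √1,300 − 1.264)/0.6440 = 0.837, so 79.9%.

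The stated size reproduces.

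**What exact week adds beyond its bands**

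Assumption: weeks are spread evenly over 16 to 30.
- Total variance of week = (15² − 1)/12 = 18.67.
- Variance within a five-week band = (5² − 1)/12 = 2.
- Share left within bands = 2/18.67 = 0.107, so the bands already carry about 89%.
- Added R² = r² × 0.107, where r is the correlation of week with the outcome. The documents give no r. For r = 0.1, 0.2 and 0.3 the result is 0.001, 0.004 and 0.010.

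**What exact age adds beyond its bands**

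Assumption: mean age 28, SD 6, limited to 18–45, split between 30 and 31.
- Share left within bands = 0.374 (by simulation).
- Added R² = r² × 0.374. For r = 0.1, 0.2 and 0.3 the result is 0.004, 0.015 and 0.034.

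**Effect on power**

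Effective n per arm = 1,300/(1 − R²), and the standard error shrinks by the factor √(1 − R²). The combined rows add the two R² values, which assumes that week and age are uncorrelated within strata.

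| Added to the model | Added R² | Effective n per arm | Power |
|---|---|---|---|
| Nothing (unadjusted) | 0 | 1,300 | 79.9% |
| Week, r = 0.3 | 0.010 | 1,313 | 80.3% |
| Age, r = 0.3 | 0.034 | 1,346 | 81.2% |
| Both, r = 0.1 | 0.005 | 1,307 | 80.1% |
| Both, r = 0.3 | 0.044 | 1,360 | 81.6% |

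With both variables at r = 0.3, the standard error falls by 1 − √0.956 = 2.2%. Most of the gain comes from age. Squared terms could add a little more, and I have not credited any.

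**The case against.** The strongest reply is that stratum fixed effects with robust standard errors are a valid analysis of this stratified design. They are fixed in advance and use variables known for everyone. The extra terms are worth perhaps 0 to 2 power points on inputs that the documents do not supply. In addition, 79.9% is an unadjusted two-proportion figure, which gives no credit for variance already absorbed by the stratum dummies, and its distance from 80% is rounding. All of this stands. It limits the point to efficiency but does not remove it, because week and age are also known for everyone and can equally be fixed in advance.

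A reader might be tempted by four stronger readings, which the documents do not support.

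- **Week 16 against week 20 as time for visits.** One might argue that a woman registering earlier in a band has had less time to attend antenatal care. The outcome counts visits over the whole pregnancy (Primary Outcomes, Table 5), so time elapsed at registration does not limit it. Any link would have to run through something else, such as care-seeking or length of exposure to messages.
- **Number of children and education as ready covariates.** Their source and timing are not stated. The baseline survey is optional, follows randomisation, and runs by USSD in the SMS arm but by WhatsApp in the others, so response could differ by arm. Number of children also changes with the index birth if it is asked at endline. Letting their use depend on a test of response by arm would weaken pre-specification.
- **A gain of 4 points or more.** That needs an added R² of about 0.10 (83.8% power). Nothing in the documents supports such a value, and week and age do not reach it under the assumptions above.
- **A remedy for multiplicity or weighting.** The power calculation allows for neither the false discovery rate adjustment nor the weights. Those are separate matters, and a gain of this size would not offset them.

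**Conclusion.** The point holds as a minor improvement in efficiency. The model adjusts only for coarse bands of two variables that are collected from every woman before allocation. Using the finer values should raise power from 79.9% to somewhere between 80.1% and 81.6%.

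That range rests on assumed correlations of 0.1 to 0.3, evenly spread weeks and an assumed age distribution. It also depends on the form of the outcomes, which are binary under Sample Size and Primary Outcomes but counts in Table 5. It assumes that registration stores week and age more finely than the bands. The age-35 subgroup cut and the weights suggest this, but the plan does not say it outright. The validity of the planned analysis is not in question.

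**What to change.** In the Primary Specification, add gestational week at registration and age in years at registration, each as a linear and a squared term, beside the existing stratum dummies. State that both are the values recorded before randomisation. Report the strata-only model as a sensitivity analysis.

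Do not add number of children or education to the primary model unless the plan shows that they are measured before treatment and available for all analysed women.

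The cost is four regression terms and a sentence or two of text, with no new data. The change should be made before outcome data are examined.
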